The study physician will review outcome measures and results based on the first 10 weeks of the study, which will be compiled in Excel by the study coordinator before the visit (using the template "Exit Summary" excel document in dopamine>Lithium in FTD>Exit Summaries). The physician will then discuss the possibility of whether to continue the dose of lithium, if the participant was an active responder, or whether to begin a low dose of lithium if the participant was on placebo. If the study physician is not the primary physician for the participant, this decision must be discussed with the referring physician, to whom the study physician may make a recommendation. When referring to outside physicians, it is important to thoroughly inform them of the plan for lithium treatment and the target therapeutic levels for this population. The study coordinator is expected to remain blinded even after the participant completes the trial.

Adverse Events and Protocol Deviations

Adverse events and serious adverse events will be carefully monitored, recorded, and reported in this study. An adverse event (AE) is an unexpected medical occurrence or worsening of symptoms, which does not necessarily have a causal relationship with study treatment. Study physicians should monitor gait disturbances or tremor of at least moderate intensity as well as falls in particular for this study. A serious adverse event (SAE) is a medically serious event, any event requiring hospitalization, and death.

Each patient that has an AE or SAE reported will have an AE log filed in their research chart. Both AE and SAE are to be recorded on the AE log version date 07/18/2016. AE logs are to-data forms for this study. Hardcopy AE forms are rewritten each time new information about the event is

made available, with all revisions kept in paper research charts. However, the database AE form will only contain information reflecting the final resolved event or last recorded information once the patient has left the protocol. Information regarding the treatment provided, outcome, and presumed relationship to study drug will be updated as new information becomes available. Site PIs will sign the bottom of the AE logs for their own site once the patient has exited the protocol.

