Outcome measures and covariates. Primary outcome: agitation/aggression score (domain score on the Neuropsychiatric Inventory (NPI), continuous measure from 0-12, longitudinal); Secondary outcome: response (dichotomous, based on 30% decrease in NPI core score (sum of domains for motor activity and agitation/aggression) plus a CGI-C score of much improved or very much improved, longitudinal); Exploratory outcome motor activity score on the NPI. Covariates/Predictor variables: 1) demographic characteristics (e.g., gender, race, age); 2) baseline measures of the corresponding outcomes. Other Measures:1) tolerability, as measured by emergent side effects (TESS scores and adverse events) over the course of the 12 week trial; 2) brain derived neurotrophic factor (BDNF) serum levels.

Sample size and randomization: The randomization will be carried out by the statistician and implemented by the pharmacist, who are both otherwise independent of the research team. The randomization sequences will be balanced in blocks of random size to prevent clinicians from guessing what the next patient's treatment might be.

Modeling longitudinal data and testing hypotheses. Modeling longitudinal data and testing hypotheses. All tests will be two-sided; α =0.05; intent-to-treat with data included for all patients with ≥1 post-baseline assessment. We will use generalized linear mixed models (GLMMs; SAS PROC GLIMMIX) for longitudinal data to evaluate study aims. Models will include fixed effects for treatment group, time, group x time interaction, and any baseline covariates found to be unbalanced despite randomization. Prior to analysis, we will examine all variables at all time points for outliers and inconsistencies and examine their distributions.⁴¹⁻⁴³

Primary hypothesis: *Lithium will significantly reduce agitation/aggression as compared to placebo.*

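### The adverse-event definition is limited to unexpected occurrences, so non-serious known lithium effects may be left off the AE log and its between-arm comparison shrunk towards no difference

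*Combined protocol and SAP*

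**What the plan says.** Adverse Events and Protocol Deviations gives the definition: "An adverse event (AE) is an unexpected medical occurrence or worsening of symptoms". The rest of that sentence says a causal link with study treatment is not required. The section continues: "Study physicians should monitor gait disturbances or tremor of at least moderate intensity as well as falls in particular for this study". Serious events are defined separately: "A serious adverse event (SAE) is a medically serious event, any event requiring hospitalization, and death".

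On record keeping, the same section says that hardcopy forms are rewritten as information arrives, "with all revisions kept in paper research charts", and that "the database AE form will only contain information reflecting the final resolved event or last recorded information once the patient has left the protocol". It then names what is revised: "Information regarding the treatment provided, outcome, and presumed relationship to study drug will be updated as new information becomes available".

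Under Statistical Procedures and Data Analysis, the paragraph on outcome measures and covariates measures tolerability by "emergent side effects (TESS scores and adverse events) over the course of the 12 week trial". The Tolerability paragraph promises descriptive statistics in each arm with point estimates and confidence intervals. It specifies one test, a t-test on TESS change from baseline to week 12. TESS is listed at the screening/baseline visit and at weeks 2, 4, 6, 8, 10 and 12.

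**The concern.** Expectedness normally bears on how an event is reported, not on whether it is an adverse event. A definition that filters on it removes the events a lithium trial most needs to count: effects already known for the drug, mild enough not to be serious, and new to the patient.

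The filter acts by type of event, and those types should be commoner on lithium. Blinded staff applying the rule identically in both arms would therefore still remove more events from the lithium arm. Side effects are a stated aim of the study, and the Power Analysis paragraph makes estimates with confidence intervals, rather than tests, the main results, to prepare for a larger trial. An attenuated AE estimate would carry forward into that planning.

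**Working it through.** The plan states no adverse-event rate, so there is no safety figure to reproduce. The check is mainly a comparison of texts.

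**1. What the definition lets through.** Relatedness is explicitly not a condition; expectedness is. There are two limbs: an unexpected occurrence, or a worsening of symptoms. Whether *unexpected* also governs the second limb is unclear. If it does not, worsening of an existing symptom is an AE. A newly arising known effect that is not serious is still covered by neither limb on a literal reading.

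**2. Whether another passage restores it.**
- The monitoring sentence names tremor and gait disturbance, from moderate intensity upward, and falls. It asks physicians to watch for them and does not say that each is logged as an AE.
- The serious-event definition has no expectedness condition. As written, an expected hospitalization is a serious adverse event although it fails the definition of an adverse event. The two definitions do not nest.
- The Visit Checklists list TESS among the clinician forms but give no rule for the AE log.

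No passage says that expected effects are logged as AEs.

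**3. Where the log enters the analysis.** Tolerability has two named components, TESS scores and adverse events. The only test uses TESS. Adverse events enter through the descriptive estimates by arm; how they are to be summarised is not stated. The exposed quantity is therefore the descriptive AE estimate.

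**4. Direction and possible size.** Let pL and pP be the true proportions with a known effect on lithium and placebo, and u the share left off the log, equal in both arms because study staff are blinded. Then:

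logged difference = (1 − u) × (pL − pP)

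As placeholders only, take pL = 50% and pP = 15%. These are the response rates in the Power Analysis example, not safety rates.

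| u | Lithium logged | Placebo logged | Difference (points) |
|---|---|---|---|
| 0% | 50.0% | 15.0% | 35.0 |
| 25% | 37.5% | 11.25% | 26.25 |
| 50% | 25.0% | 7.5% | 17.5 |
| 75% | 12.5% | 3.75% | 8.75 |

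The ratio for the known effects themselves is unchanged (50/15 = 3.33 in every row). The absolute rates and their difference shrink. A ratio over all adverse events also moves towards 1: with b other events per patient in each arm, it is ((1 − u)pL + b) / ((1 − u)pP + b), which tends to 1 as u rises. The documents fix neither u nor the two rates, so the table shows direction and scaling only.

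**5. The database form.** It holds the final or last recorded state. The fields named as updated are treatment, outcome and relationship; intensity is not among them. The form itself is not in the documents. Whether maximum intensity and dates are kept is therefore unknown, and the paper revisions would allow both to be recovered.

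**The case against.** The best defence is that *unexpected* is ordinary usage for untoward. Nothing ties it to a reference list of known lithium effects. Causality is waived, worsening is a separate limb, and the next sentence singles out tremor, gait and falls. No one is told to leave known effects out, and staff who read the whole paragraph might well log them. This is a fair account of what could happen in practice, and it is why u may be small. It does not change the written definition, which leaves the decision to each reader.

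The second defence is TESS, and most of it stands. TESS is collected at baseline and at every later visit without an expectedness filter, and it carries the only formal safety test. A reader might infer that known effects vanish from the safety comparison altogether; the documents do not support that. Nor can TESS be set aside as covering only its listed symptoms, because its item list is not in the documents and its coverage cannot be judged either way. What remains is that the plan names adverse events as a component in their own right, and TESS scores do not repair an undercount there.

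A reader might also infer that reports to the funder, IRB and DSMB would look too safe. The safety item listed for the funder, and the IRB route described in the adverse-events section, concern serious adverse events, whose definition has no expectedness condition. What event data the DSMB receives is not stated.

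**Conclusion.** The point holds for the AE log only. As written, the definition permits new, non-serious, known lithium effects to go unlogged. If staff follow it, the descriptive AE comparison is attenuated towards no difference. This rests on two assumptions: that the expected effects are commoner on lithium, and that the unlogged share is similar in the two arms. The size cannot be determined from the documents.

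Two stronger readings should be resisted. One is that a real difference would be wiped out; that requires every known effect in both arms to be left off, including those that physicians are told to watch. The other is that the database loses peak severity. "the database AE form will only contain information reflecting the final resolved event or last recorded information" makes that a possibility to check, not a finding, since the form's fields are not shown, intensity is not among the fields named as updated, and all paper revisions are kept.

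The efficacy analyses, the TESS test and serious-event reporting are untouched. This is a modest defect in a named measure, worth correcting because the remedy is small.

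**What to change.** Replace the definition with: 'any untoward medical occurrence or worsening of symptoms, whether or not expected or related to study drug'. Record expectedness as a separate field on the AE form.

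When the database AE form is finalised, check that maximum intensity and onset and stop dates are carried over from the retained paper revisions. Add those fields only if they are absent.

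If patients have already been followed under the present wording, a blinded review of charts against visit-level TESS would show whether known effects were left off the log.

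The cost is one sentence, one field and a form check. The downside is more AE entries for coordinators. The change affects documentation only and alters no clinical rule.

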NCT02862210

Low-dose lithium for the treatment of behavioral symptoms in Frontotemporal Dementia Standard Operating Procedures Manual Version date 31May2021

Introduction

The Alzheimer's Drug Discovery Foundation funded a study titled "Low-dose lithium for the treatment of behavioral symptoms in Frontotemporal Dementia," which examines the efficacy and side effects of low dose lithium treatment for agitation/aggression/repetitive behaviors in 60 patients with FTD in a randomized, double blind, placebo-controlled 12-week trial.

Lithium carbonate or placebo will be started at an oral dose of 150 mg daily, with subsequent dose titration to 300mg/day at the 2-week visit, 450mg/day at the 4-week visit, and 600mg/day (maximum daily dose) at the 6-week visit. This upward dose titration will occur if clinically indicated, tolerated by the patient, and based on real/sham lithium blood level. An absence of response at lower doses without intolerable side effects is defined as clinically indicated. Assessments will take place at study entry (0 weeks), 2, 4, 6, 8, and 12 weeks, and the time-point of protocol exit for dropouts. Lithium levels will be drawn approximately 12-14 hours after the last dose.

Our primary outcome measures will be the Neuropsychiatric Inventory and the Clinical Global Impression scales.

Optimal target serum levels of lithium will be between 0.2 to 0.6 mmol/L due the risk of dropout due to lithium toxicity at higher levels. Clinical response of symptoms and side effects experienced by the patient will be primary in guiding oral lithium dose adjustment, and will override the information obtained from serum lithium levels if such a choice needs to be made.

This study will provide useful data on the efficacy and side effects of low-dose lithium treatment for FTD patients with symptoms of agitation/aggression, and possibly for other behavioral symptoms such as aberrant motor behaviors. The potential utility of lithium would provide an alternative for patients who show no/minimal response to or experience intolerable side effects while on antidepressants and antipsychotics.

During COVID, it was decided that the protocol would be updated to allow for a portion of the study visits to occur remotely. This was largely to reduce risks to participants once the study reopened (I.e. to minimize time traveling to a hospital), but also, we hoped this would make the study less burdensome to patients and study partners moving forward.

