-Drug IDs will be assigned by the pharmacy CUMC Drug ID#: LF101-LF199 (last two digits of drug ID are one lower than the last two digits of the subject ID, e.g. subject ID #1017 and drug ID #LF116)

Each time a new patient is randomized, the pharmacy must email the updated randomization tables to the unblinded physician, [name]. The pharmacist should be reminded of this instruction when the randomization form is sent.

The pharmacy should be instructed to mail the kit directly to the research participant. They should not include the unblinding envelope in the kit. The coordinator/physician should review dosing instructions with the caregiver at the time of the visit (starting dose = 1 pill daily in the evening, use the same bottle between for the full two week interval). The coordinator should notify the caregiver once the study drug has shipped and should ask the caregiver to contact them when it arrives. Once the kit has been received, the coordinator should review these instructions with the caregiver by phone, and the dosing should begin that day. At this time, the Week 2 virtual visit may be scheduled to occur approximately 2 weeks after the participant begins the study medication.

Sample email to pharmacy upon randomization: *"Please find attached a new study drug order.*

Please mail the study drug kit to directly to the participant at the listed address. Please do not include an unblinding envelope. The cost of this can be billed to our study protocol, NYSPI #7310, Lithium in FTD.

Week 2 Visit

Typically, this will be a virtual visit with no at-home blood draw. If there are clinical concerns (e.g. significant side effects), this can be converted into an in-person visit, which is true for all visits that typically occur virtually.

The visit should be scheduled in advance, and a calendar invitation (with a zoom link and schedule) should be sent to both the study physician and the caregiver.

At the visit, the oral dose may be adjusted from 150 mg/day up to 300 mg/day. This will be based on assessments and evaluation of the following:

- Clinical response
- Side effects

The following assessments will be completed at the week 2 visit:

- Concomitant Medications
- NPI
- Stereotypic and ritualistic behaviors
- CGI Behavior (CGI-S, CGI-C)
- CGI Global (CGI-S, CGI-C)
- TESS

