- Medication compliance (the study partner will be asked to count on camera the number of pills remaining in the bottle they used for the first two weeks to ensure correct dosing. 14 pills should remain in the bottle if the medication has been taken for 14 days).

The week 2 visit is estimated to take 60 minutes on average.

Color-codes	
Coordinator	
Physician	
Time	Assessment
20 minutes	Vitals, TESS, Concomitant Meds, CGI,
	with Patient and Caregiver.
10 minutes	Medication compliance review
30 minutes	NPI with Caregiver

At the end of the visit, caregivers should be given new dosing instructions (if the dose has increased, this would be 2 pills/day, one in the morning and one at night) and instructed to switch to a new pill bottle until the next visit (the bottle caps can be labeled with sharpie for ease). The week 4 visit should be scheduled and calendar invitations sent out.

Week 4 Visit

At week 4, the oral dose maybe adjusted from 300 mg/day up to 450 mg/day. This will be based on based on assessments and evaluation of the following:

- Clinical response
- Side effects

The following assessments will be completed at the week 4 visit:

- Concomitant Medications
- Clinical Dementia Rating (CDR)
- CGI Behavior (CGI-S, CGI-C)
- CGI Global (CGI-S, CGI-C)
- NPI
- Stereotypic and ritualistic behaviors
- TESS
- SAS
- Lawson ADL
- Zarit Caregiver Burden Interview.
- Medication compliance (the study partner will be asked to count on camera the number of pills remaining in the bottle they used for the first two weeks to ensure correct dosing.
 0 pills should remain in the bottle if the medication has been taken for 14 days at 300mg/day).

The week 4 visit is estimated to take 70 minutes on average.

Color-codes	
Coordinator	
Physician	
Time	Assessment
20 minutes	Vitals, TESS, Concomitant Meds, Simpson-Angus, CDR, CGI, Lawton with Patient and Caregiver. Lithium Prescription
10 minutes	Medication compliance review
40 minutes	NPI, Zarit with Caregiver

Week 6 Visit

At week 6, blood for serum lithium level will be drawn and the oral dose subsequently adjusted from 450 mg/day up to 600 mg/day if needed. This will be based on the following assessments and evaluations:

- Clinical response
- Side effects
- Blinded lithium level obtained from the unblinded physician

The following assessments will be completed at the week 6 visit:

- Concomitant Medications
- CGI Behavior (CGI-S, CGI-C)
- CGI Global (CGI-S, CGI-C)
- NPI
- Stereotypic and ritualistic behaviors
- TESS

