- Medication compliance (the study partner will be asked to count on camera the number of pills remaining in the bottle they used for the first two weeks to ensure correct dosing. 14 pills should remain in the 2nd bottle if the medication has been taken for 14 days at 450mg/day).

Completed by ExamOne:

- Vital signs
- Serum lithium level
- Safety labs

The week 6 visit is estimated to take 1.5-2 hours on average.

Color-codes	
Coordinator	
Physician	
Time	Assessment
10 minutes	TESS, Concomitant Meds, CGI, with
	Patient and Caregiver.
30 minutes	NPI with Caregiver
10 minutes	Medication compliance review

Vital signs and blood draw will be scheduled separately and completed by the Exam One mobile phlebotomy team, who will ship samples directly to the CALM lab for processing.

Week 8 Visit

At week 8, blood for serum lithium level will be drawn and the oral dose subsequently adjusted up to 600 mg/day if needed based on the following assessments and evaluations:

- clinical response
- side effects
- Blinded lithium level from the unblinded physician.

The following assessments will be completed at the week 8 visit:

- Concomitant Medications
- CDR
- CGI Behavior (CGI-S, CGI-C)
- CGI Global (CGI-S, CGI-C)
- NPI
- Stereotypic and ritualistic behaviors
- TESS
- SAS
- LADL
- Zarit Caregiver Burden Interview.
- Medication compliance (the study partner will be asked to count on camera the number of pills remaining in the bottle they used for the first two weeks to ensure correct dosing.
 0 pills should remain in the 2nd bottle if the medication has been taken for 14 days at 600mg/day).

Completed by ExamOne:

- Vital signs
- serum lithium level

The week 8 visit is estimated to take 50 to 60 minutes on average.

Color-codes	
Coordinator	
Physician	
Time	Assessment
20 minutes	TESS, Concomitant Meds, Simpson-
	Angus, CDR, CGI, Lawton with Patient
	and Caregiver. Lithium Prescription
40 minutes	NPI, Zarit with Caregiver
10 minutes	Medication Compliance Review

Vital signs and blood draw will be scheduled separately and completed by the Exam One mobile phlebotomy team, who will ship samples directly to the CALM lab for processing.

Week 10 Visit

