- Schedule visit with participant for 2 weeks after they receive the study drug kit. During this call, also confirm dosing schedule (1 pill in evenings) and ask them to use the same bottle during the 2 week period.
- □ Create zoom link & send along with date/time of visit & visit schedule to the study partner
- Send a calendar invitation to the study physician. In the calendar invitation, include:
 - o Zoom link
 - Links to clinician forms within REDCap for the correct subject/week
 - o List of clinician forms: Treatment emergent symptoms, CGI-Severity, CGI-Change
 - Current subject medication dose, anticipated dose change after visit, & any other relevant information

During visit:

- □ Complete medication compliance check: have study partner count pills remaining in the bottle they have been using. Each bottle contains 28 pills, so calculate the number of pills that should be remaining (14 if 2 weeks from kit receipt)
- On REDCap, complete the following forms with the study partner:
 - Visit registry, concomitant meds, NPI, Stereotypic/Ritualistic behaviors, study drug issue/return log

Post-visit:

- □ If no contradictions per study clinician, instruct participant/study partner to increase dose to 300mg/day (one pill mornings, one pill evenings), using a new bottle.
- □ Schedule Week 4 visit with participant for 2 weeks after their week 2 visit.
- Obtain clinician signature on REDCap study drug issue/return log, resolve any missing data from clinician forms

Week 4

Pre-visit:

- □ Create zoom link & send along with date/time of visit & visit schedule to the study partner
- Send a calendar invitation to the study physician. In the calendar invitation, include:
 - o Zoom link
 - o Links to clinician forms within REDCap for the correct subject/week
 - List of clinician forms: Treatment emergent symptoms, CGI-Severity, CGI-Change, Simpson-Angus, Lawton, CDR
 - Current subject medication dose, anticipated dose change after visit, & any other relevant information

During visit:

- □ Complete medication compliance check: have study partner count pills remaining in the bottle they have been using. There should be 0 remaining if 14 days have passed since the previous visit (and they were taking 2 pills daily).
- □ On REDCap, complete the following forms with the study partner:
 - Visit registry, concomitant meds, NPI, Stereotypic/Ritualistic behaviors, Zarit Burden Interview, study drug issue/return log

Post-visit:

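### The post-visit checklist dose lines at weeks 2, 4, 6 and 8 leave out the no-response condition that the Introduction sets for a dose increase (minor conflict in a working instruction)

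*Combined protocol and SAP*

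**What the plan says.** The Introduction makes upward titration conditional on clinical indication, tolerability and the real or sham level. It defines the first of these: "An absence of response at lower doses without intolerable side effects is defined as clinically indicated". It also ranks the inputs: "Clinical response of symptoms and side effects experienced by the patient will be primary in guiding oral lithium dose adjustment", and this overrides the serum level if the two disagree.

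The visit sections agree with that rule. Week 2 Visit is permissive, "At the visit, the oral dose may be adjusted from 150 mg/day up to 300 mg/day", and its dosing instruction allows for no change: "if the dose has increased, this would be 2 pills/day". Week 4 Visit is permissive in the same way. In Week 6 Visit the dose is "adjusted from 450 mg/day up to 600 mg/day if needed", and in Week 8 Visit it is "adjusted up to 600 mg/day if needed based on the following assessments and evaluations". All four sections list clinical response and side effects as bases; weeks 6 and 8 add the blinded level.

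The post-visit items under Visit Checklists read differently. Week 2 says "If no contradictions per study clinician, instruct participant/study partner to increase dose to 300mg/day", and week 4 repeats the form for 450 mg/day. Weeks 6 and 8 keep the no-objection clause and add that the real or sham level must lie in the target window before the step to 600 mg/day; week 8 also offers staying at dose. None of the four lines mentions response.

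**The concern.** Under the Introduction an increase needs a positive finding that the patient has not responded. Under the checklist it goes ahead unless the clinician objects. The checklist is what the coordinator has in hand when instructing the caregiver, so a hold that nobody voices becomes an increase.

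The level condition at weeks 6 and 8 does not replace the missing one. It relies on the level and is silent on response, although the Introduction puts response first.

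What is at stake is avoidable lithium exposure in a tolerant patient who has already responded and, at weeks 6 and 8, a level pushed toward or past the top of the target range. The Introduction ties that range to tolerability: "Optimal target serum levels of lithium will be between 0.2 to 0.6 mmol/L due the risk of dropout due to lithium toxicity".

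**Working it through.** The plan states no figure on this point, so the check compares texts and then gives a per-patient illustration.

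**Step 1. Same situation, two instructions** (patient tolerates the dose, physician says nothing):

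| Situation | Introduction rule | Checklist line, read literally |
|---|---|---|
| Week 2 or 4, responder | no increase | increase |
| Week 6, responder, level in window | no increase | increase to 600 mg/day |
| Week 6, non-responder, level below window | increase indicated | no increase instructed |
| Week 8, at 450 mg/day | as week 6 | as week 6, except that staying at dose is also offered |

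The gap is clearest at weeks 2 and 4. The assay list under Biological Sample Collection has no lithium level at those visits, and the blinding section's physician-choice step starts from a reported level. (That section does mention weeks 2 and 4 as draw visits, in parentheses the first time. If a level were drawn then, the step would apply.)

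**Step 2. Pills for one affected patient.** Inputs: 150 mg pills, 84 days, and the dose steps in the Introduction, taken at exact two-week visits.

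- Held at 150 mg/day: 84 × 1 = 84
- Held at 300 from week 2: 14 × 1 + 70 × 2 = 154
- Held at 450 from week 4: 14 × 1 + 14 × 2 + 56 × 3 = 210
- To 600 at week 6: 14 × 1 + 14 × 2 + 14 × 3 + 42 × 4 = 252
- To 600 at week 8: 14 × 1 + 14 × 2 + 28 × 3 + 28 × 4 = 238

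One missed hold, then held:

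- week 2: 154/84 = 1.83
- week 4: 210/154 = 1.36
- week 6: 252/210 = 1.20
- week 8: 238/210 = 1.13

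Upper bound, every later hold missed: 252/84 = 3.0 for a patient who should have stayed at 150, and 252/154 = 1.64 for one who should have stayed at 300.

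**Step 3. Level after the last step.** Assumption, not in the documents: the level rises in proportion to dose. Then 600/450 = 1.33, and an in-window level above 0.6/1.33 = 0.45 mmol/L projects above 0.6, to at most 0.6 × 1.33 = 0.80. If the factor were 1.2, the threshold would be 0.50 and the maximum 0.72; if 1.5, 0.40 and 0.90. The week 8 draw would show this after a week 6 increase, and the week 10 draw that the checklist calls for would show it after a week 8 increase.

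These figures describe one patient whose hold was missed. The documents give neither the share of early responders nor how often a hold would be missed, so the figures cannot be scaled to the trial.

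**The case against.** The strongest reply is that the checklists are a reference aid. Their preamble sends the reader back to the earlier sections for detail, and those sections name clinical response at all four visits. The blinding section goes further: once a level is reported, the physician chooses to change or continue the dose, and only then does the coordinator call the caregiver. At weeks 6 and 8 a coordinator following that procedure has no silence to act on. The physician rates CGI at each of these visits, is told beforehand of the current dose and the expected change, and signs the drug log. A clinician's objection can naturally include a response already achieved.

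Most of this stands, and it limits the harm. It does not remove the mismatch. The titration criterion is the decision rule itself, and the lines give a dosing instruction that departs from it. Telling the physician of an expected dose change can prompt a hold, but it also presumes an increase before response is rated. The log signature is listed after the dose instruction, so it may catch an error without preventing it.

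A reader might infer that the plan forces titration to 600 mg/day. It does not. The visit sections allow no change, the blinding section provides for continuing the dose, Week 10 Visit gives a pill count for a patient at 450 mg/day, and the week 8 line can be read as a hold.

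**Conclusion.** Wrong as written, minor. Four checklist lines do not match the titration rule in the Introduction. Weeks 2 and 4 make the increase the default with no response condition. Weeks 6 and 8 tie the step to an in-window level, again with no response condition.

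The size is known only per patient: 1.13- to 1.83-fold pills for one missed hold and 3.0-fold at the extreme, assuming exact two-week visits. The projected level rests on proportionality to dose, and 0.6 mmol/L is the top of an optimal range, not a hard ceiling. The trial-level effect is unknown, and it is zero if the physician always makes the response-based decision that the other sections describe.

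A reader might also infer bias or an inflated type I error. The documents do not support that: both blinded arms follow the same dosing procedure, with sham levels for placebo.

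**What to change.** Reword the four post-visit lines along these lines: *If the study physician decides that an increase is clinically indicated (no response so far, no intolerable side effects) and, at weeks 6 and 8, the real or sham level is not above the target window, increase to X mg/day; otherwise continue or reduce the current dose.*

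Setting the level condition as not above the window, in place of within it, lets a non-responder with a low level be raised. The same edit should say which window applies, since the Introduction gives 0.2 to 0.6 mmol/L and the blinding section 0.4 to 0.6.

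The cost is four lines and a staff note. NPI and CGI-C are already collected at these visits, so no assessment or visit is added.
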